8.1.5 Clinical Laboratory and Other Safety Evaluations

A change in the value of a clinical laboratory, vital sign, or ECG assessment can represent an AE if the change is clinically significant or if, during treatment with the IP, a shift of a parameter is observed from a normal value to an abnormal value, or there is a further worsening of an already abnormal value. When evaluating such changes, the extent of deviation from the reference range, the duration until return to the reference range (either while continuing treatment or following IP discontinuation), and the range of variation of the respective parameter within its reference range must be taken into consideration.

At the end of the treatment phase, for participants who complete the study and do not progress to an IV anesthetic for seizure suppression, if there are abnormal clinical laboratory, vital sign, or ECG values that were not present in the pretreatment assessments closest to the start of IP initiation, further investigations should be performed until the values return to within the reference range or until a plausible explanation (e.g., concomitant disease) is found for the abnormal values.

The investigator should decide, based on the above criteria and the clinical condition of a participant, whether a change in a clinical laboratory, vital sign, or ECG parameter is clinically significant and therefore represents an AE.

8.1.6 Pregnancy

As this study allows for pre-consenting of participants, all pregnancies are to be reported from the time of IP initiation until the defined follow-up period stated in [Section 7.1](#).

Any report of pregnancy for any female study participant or the partner of a male study participant must be reported within 24 hours to the Marinus Drug Safety vendor using the Pregnancy Report Form. If a participant has a positive test result, it will be at the investigator's discretion to weigh the risks versus benefits for continued participation.

Every effort should be made to gather information regarding the pregnancy outcome and condition of the infant. It is the responsibility of the investigator to obtain this information within 30 calendar days after the initial notification and approximately 30 calendar days after delivery.

Pregnancy complications such as spontaneous abortion/miscarriage or congenital abnormality are considered SAEs and must be reported as outlined in [Section 8.2](#) of the protocol using the Marinus SAE Fax Cover Letter. Non-serious AEs are to be reported as per clinical eCRF Completion Guidelines. Note: An elective abortion is not considered an SAE.

In addition to the above, if the investigator determines that the pregnancy meets serious criteria, it must be reported as an SAE to the Marinus Drug Safety vendor as outlined in Section 8.2 of the protocol using the Marinus SAE Fax Cover Letter. The test date of the first positive serum/urine β -human chorionic gonadotropin test or ultrasound result will determine the pregnancy onset date.

8.1.7 Medication Errors and Other Reportable Information

Medication errors made in prescribing, dispensing, administering, or use of an IP must be reported as protocol deviations. An overdose is a medication error and is defined as administration of IP exceeding the prespecified total daily dose of the IP which for this study is set by a 50 g/day (1.25 g/kg/day in participants weighing <40 kg) Captisol® limit which corresponds to a maximum of 833 mg/day (20.825 mg/kg/day in participants weighing <40 kg) ganaxolone.

If a medication error results in a Captisol®/ganaxolone overdose, this is a protocol deviation that may have the potential to affect the safety of the affected participant. The administration of lower doses of the IP as a result of an IP rate decrease or as part of IP discontinuation are not considered medication errors and are permitted by protocol.

In addition to medication errors the following events are considered other reportable information and are reportable to the Marinus Drug Safety vendor within 15 days of awareness of the event using the Medication Errors and Other Reportable Information Report Form. A copy of the Report Form (and any applicable follow-up reports) must also be sent to the Medical Monitor using the details specified in the emergency contact information section at the beginning of the protocol:

- Accidental exposure
- Lactation exposure
- Product Misuse

All IP provided in this study will be administered by appropriate site staff.

8.2 Serious Adverse Event Procedures

8.2.1 Reference Safety Information

The Reference Safety Information for this study is the Ganaxolone IB, which the Sponsor has provided under separate cover to all investigators.

8.2.2 Reporting Procedures

All initial and follow-up SAE reports must be reported by the investigator to the Marinus Drug Safety vendor within 24 hours of the first awareness of the event. Note: The 24-hour reporting requirement for SAEs does not apply to reports of medication errors and other reportable information (see [Section 8.1.7](#)) unless the event results in an SAE.

The investigator must complete, sign, and date the Marinus SAE Fax Cover Letter and verify the accuracy of the information recorded on the form with the corresponding source documents (Note: Source documents are not to be sent unless requested) and fax or email the form to the Marinus Drug Safety vendor. A copy of the Marinus SAE Fax Cover Letter (and any applicable

follow-up reports) must also be sent to the Medical Monitor using the details specified in the emergency contact information section of the protocol.

8.2.3 Serious Adverse Event Definition

An SAE is any untoward medical occurrence (whether considered to be related to IP or not) that at any dose:

- Results in death
- Is life-threatening. Note: The term “life-threatening” in the definition of “serious” refers to an event in which the participant was at risk of death at the time of the event; it does not refer to an event that hypothetically might have caused death if it were more severe.
- Requires inpatient hospitalization or prolongation of existing hospitalization. Note: Hospitalizations, which are the result of elective or previously scheduled surgery for preexisting conditions that have not worsened after initiation of treatment, should not be classified as SAEs. For example, an admission for a previously scheduled ventral hernia repair would not be classified as an SAE; however, a complication resulting from a hospitalization for an elective or previously scheduled surgery that meets serious criteria must be reported as an SAE.
- Results in persistent or significant disability or incapacity
- Is a congenital abnormality or birth defect
- Is an important medical event. Note: Important medical events that may not result in death, be life threatening, or require hospitalization may be considered an SAE when, based on appropriate medical judgment, they jeopardize the patient and may require medical or surgical intervention to prevent one of the outcomes listed in this definition. Examples of such medical events include allergic bronchospasm requiring intensive treatment in an emergency room or at home; blood dyscrasias that do not result in inpatient hospitalization, or the development of drug dependency or drug abuse.

8.2.4 Serious Adverse Event Collection Time Frame

As this study allows for pre-consenting of participants, all SAEs (regardless of relationship to study) are collected from the time of IP initiation until the final study follow-up visit/contact stated in [Section 7.1](#) and must be reported to the Marinus Drug Safety vendor within 24 hours of the first awareness of the event.

In addition, any SAE considered “related” to the IP and discovered by the investigator at any interval after the study has completed must be reported to the Marinus Drug Safety vendor within 24 hours of the first awareness of the event.

8.2.5 Serious Adverse Event Onset and Resolution Dates

The onset date of the SAE is defined as the date the event meets serious criteria. The resolution date is the date the event no longer meets serious criteria, the date the symptoms resolve, or the date the event is considered chronic. In the case of hospitalizations, the hospital admission and discharge dates are considered the onset and resolution dates, respectively.

In addition, any signs or symptoms experienced by the participant following IP initiation or leading up to the onset date of the SAE, or following the resolution date of the SAE, must be recorded as an AE, if appropriate.

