- Investigational product discontinuation does not affect continued participation in the study. All participants should be followed, regardless of early discontinuation of IP, until they reach the final study follow-up visit/contact unless consent is withdrawn.
- In cases when IP discontinuation is being considered (e.g., severe sedation), when possible, the Medical Monitor should be contacted prior to infusion termination.
- If the decision is made to restart IP, the infusion should be restarted at the rate matching the rate at the corresponding nominal time, counted from the start of the IP infusion on Day 1. Investigational product bolus or "catch-up" dose to deliver the IP that was missed during the interruption should not be administered.

Dose (infusion rate) increases above those specified in the protocol are not allowed at any time during infusion. This is to ensure daily Captopsol® and ganaxolone limits are maintained at \leq 50 g/day (1.25 g/kg/day in participants weighing <40 kg) and \leq 833 mg/day (20.825 mg/kg/day in participants weighing <40 kg), respectively.

Methodology:

This is a double-blind, randomized, placebo-controlled study to evaluate the efficacy and safety of ganaxolone IV solution in SE, with the option to transition the study to an open-label phase to obtain additional safety data.

Screening, duration of the treatment, and follow-up periods, as well as the study schedule, remain the same for participants enrolled under either the double-blind or open-label phases.

As previously described, IP will be added to standard of care after failure of two or more antiseizure treatments (benzodiazepine and one IV AED or two IV AEDs).

Potential participants may be identified in the emergency department, ICU, or other units in the hospital, and will be consented/assented and then screened for inclusion/exclusion criteria prior to being randomized to start IP treatment. Investigational product will be administered as a 3-minute bolus that will be started with a continuous IV infusion of IP lasting for 36 hours and followed by a 12- hour taper. After the IP has been discontinued, the follow-up period assessments/procedures will be collected every 24 hours through 120 hours (or until hospital discharge) and at the time of hospital discharge followed by weekly follow-up visits/contacts at Week 1, 2, 3 and 4.

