8.1.4 Symptoms of the Disease Under Study

Symptoms of the disease under study should not be classified as AEs as long as they are within the normal day to day fluctuation or expected progression of the disease and are part of the efficacy data to be collected in the study; however, significant worsening of the symptoms should be recorded as an AE. Specifically, SE signs and symptoms that were present at study entry and that varied in intensity over the duration of study treatment are not considered AEs unless in the investigator’s opinion there is an *unexpected* worsening of the events. However, if all seizure activity resolved and the participant returned to baseline status, but SE recurred, the event would then be recorded as an SAE.

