3.3.1 Adverse Events

Adverse events (AEs) will be coded by MedDRA® version 22.0 or higher and grouped by SOC and PT. The verbatim term will be included in the AE listings. Except where indicated, the summary tables will include only TEAEs. All AEs, treatment-emergent or otherwise, will be presented in participant data listings.

A treatment-emergent adverse event (TEAE) is defined as an AE that occurred or worsened at the time of or following IP initiation. To allow differentiation between the study period in which an AE occurred, two categories are defined based upon onset date. Adverse events that had onset dates prior to the IP initiation are considered "prior." Adverse events with onset dates on or after IP initiation and up to the end of the follow-up period are considered "on-therapy" or equivalently "treatment emergent". Adverse events with onset dates prior to the IP initiation but that worsen after IP starts will be considered treatment emergent.

An overview table, including number and percentage of participants with AEs, TEAEs, TEAEs by highest severity, serious TEAEs, study drug related TEAEs, TEAEs leading to IP discontinuation, and TEAEs leading to death will be provided.

In addition, the following summary tables will be provided:

- TEAE by SOC and PT
- TEAEs by PT
- TEAE by SOC, PT, and severity
- Study drug related TEAE by SOC and PT
- Serious TEAE by SOC and PT
- Serious and drug-related TEAE by SOC and PT
- TEAEs leading to study drug discontinuation by SOC and PT
- TEAEs leading to withdrawal

All AE tables will be sorted by SOC and PT in decreasing frequency of the number of participants in the GNX-treated group. If frequency ties, the sorting will be alphabetic.

A participant having the same AE more than once will be counted only once in the number and percentage of participants' calculation for that AE. Similarly, if a participant had more than one AE in a SOC, the participant will be counted only once in the number of participants with an AE for that SOC. If a participant has the same AE on multiple occasions, the highest severity (severe > moderate > mild) recorded for the event will be presented in the AEs by severity table.

Adverse event listing will be provided for all TEAE, serious TEAEs, TEAE related to IP, TEAE leading to study drug discontinuation, AEs leading to withdrawal, and participants who died during the study.

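### Protocol 8.2.5 can date an SAE that prolongs the index hospital stay to the admission date, before IP, and SAP 3.3.1 can then leave it out of the serious-TEAE tables

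*Protocol*

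**What the plan says.** Protocol 8.2.5 contains two onset rules. The general one is: "The onset date of the SAE is defined as the date the event meets serious criteria". The specific one is: "In the case of hospitalizations, the hospital admission and discharge dates are considered the onset and resolution dates, respectively". The section does not mention prolongation and does not set aside the stay during which IP is given. Its second paragraph asks that "any signs or symptoms experienced by the participant following IP initiation or leading up to the onset date of the SAE", or after the SAE resolves, be recorded as an AE where appropriate.

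Protocol 8.2.3 makes an event serious if it "Requires inpatient hospitalization or prolongation of existing hospitalization". Admission and prolongation share one bullet, and the bullet's explanatory note speaks of hospitalizations in general. Protocol 8.2.4 says that SAEs "are collected from the time of IP initiation until the final study follow-up visit/contact".

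On setting, the Synopsis (Methodology) says: "Potential participants may be identified in the emergency department, ICU, or other units in the hospital". In Protocol Table 1, hospital discharge is an assessment in the follow-up after IP discontinuation.

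SAP 3.3.1 defines a TEAE as an AE that arose or worsened at or after IP initiation. It then forms two categories from the onset date. For the first it says: "Adverse events that had onset dates prior to the IP initiation are considered" *prior*. Onset on or after IP initiation makes the event treatment emergent, as does pre-IP onset followed by worsening. Summary tables hold TEAEs only unless marked otherwise, while listings hold all AEs.

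**The concern.** Dating an SAE by admission suits an outpatient trial, where going into hospital is the event. Here the participant is usually in hospital already. Until discharge, an inpatient can meet the hospitalization criterion only through prolongation, and the admission date then belongs to the original episode of status epilepticus, not to the new event.

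The period affected is the infusion and the early follow-up, which matter most for safety. Protocol 8.1.4 shows that SAEs of this kind are foreseen: "if all seizure activity resolved and the participant returned to baseline status, but SE recurred, the event would then be recorded as an SAE". Such a recurrence could easily fall within the index stay.

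If an event of this kind is dated to admission, the SAP's date-based categories can treat it as pre-existing. All of the SAP's planned serious-event tables (the overview line, serious TEAEs by SOC and PT, and serious drug-related TEAEs) are restricted to TEAEs, so the event could be missing from each of them.

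**Working it through.** The plan states no figure on this point. The check applies the 8.2.5 dating rules to each type of post-IP SAE and then applies the onset-date categories of SAP 3.3.1.

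**One invented record.** Admission 1 March, IP started 3 March, pneumonia that prolongs the stay 5 March, discharge 20 March.

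- General rule: onset is 5 March. 5 − 3 = 2 days after IP, so the event is treatment emergent.
- Admission-date rule: onset is 1 March. 1 − 3 = −2, two days before IP, so the event is *prior*.
- Difference in onset: 5 − 1 = 4 days. Recorded span under the admission-date rule: 20 − 1 = 19 days.

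The same clinical event thus falls into opposite categories according to which sentence of 8.2.5 is followed.

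**All cases.**

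| Post-IP SAE | Rule applied | Onset against IP | Onset-date category |
|---|---|---|---|
| (a) Prolongs index stay | General | After | Treatment emergent |
| (b) Prolongs index stay, admitted on an earlier calendar day | Admission date | Before | *Prior* |
| (c) Prolongs index stay, admitted from the emergency department on the IP date or later | Admission date | Same day or after | Treatment emergent |
| (d) New admission after discharge | Admission date | After | Treatment emergent |
| (e) Serious for another reason, hospitalization sentence not used | General | After | Treatment emergent |

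Only case (b) produces the loss. It needs three things together: the event is dated through the hospitalization sentence, it prolongs the index stay, and admission was on a calendar day before IP.

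**Scale of a single loss.** Protocol 3.1.1 stops randomization at 100 with 1:1 allocation, so about 100 / 2 = 50 per arm, assuming equal arms and that all received IP. One participant whose only serious TEAE is lost changes that arm's incidence by 1 / 50 = 2 percentage points. This is the effect of one loss and does not estimate how many occur.

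**The case against.** The strongest reply is that 8.2.5 can be read without conflict. The general rule comes first, the exception speaks of hospitalizations with an admission date, and 8.2.3 names prolongation as a distinct case. On that reading a prolongation follows the general rule and nothing goes wrong. This reading is available and sensible. However, the text does not state it. The hospitalization sentence is the more specific of the two, and a site could reasonably apply it to any event that is serious through the hospitalization criterion.

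The second reply is that the SAP protects the event anyway:

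- **TEAE definition.** A pneumonia that arises after IP meets the SAP's definition whatever date is recorded. That is correct, but the same paragraph then assigns categories by onset date, so for such a record the two statements disagree and a programmer must choose.
- **Worsening clause.** It does not help with a new event. Protocol 8.1.1 also has worsening of pretreatment events entered as new AEs, so the SAE record need carry no sign of worsening.
- **Collection window.** SAEs are collected only from IP initiation. This does not stop a validly collected event from carrying an earlier date, but it does make such a date an anomaly that data review (Protocol 9.1 and 9.2) might catch.
- **Separate AE entry for symptoms.** The clinical event may survive as an AE with post-IP onset, though possibly as a non-serious one.
- **Listings and Protocol 10.5.** All AEs are listed, so nothing disappears from the record. Protocol 10.5 plans an SAE summary with no explicit TEAE limit in that sentence, but the SAP's serious-event tables all carry one.

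The eCRF Completion Guidelines, which Protocol 9.2 cites, are not among the documents and may settle the dating. Expedited reporting runs from awareness of the event and is unaffected.

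**Conclusion.** The admission-date sentence does not fit a trial in which IP is given to people already in hospital. Applied to a prolongation of the index stay in someone admitted on an earlier day, it conflicts with the general rule in the same section and can move a post-IP SAE out of the serious-TEAE tables. It should be corrected before lock.

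The documents do not support three stronger conclusions that a reader might draw:

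- **That the plan necessarily dates these events before IP and removes them.** The outcome depends on which sentence of 8.2.5 the site follows and on which part of SAP 3.3.1 the programmer follows.
- **That a given percentage of SAEs is misclassified.** The documents give neither the share of SAEs dated through the hospitalization sentence nor the share of participants admitted on an earlier calendar day. They also do not show how sites read the rule. If all follow the general rule, the number is zero.
- **That lengthened SAE durations distort a planned result.** SAP 3.3.1 plans no table of AE duration, so the effect would be confined to recorded dates.

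The conclusion rests on the wording of 8.2.5 and SAP 3.3.1 alone, and assumes that no unseen guideline already resolves the dating.

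**What to change.** Randomization has stopped, so a protocol amendment alone would not change dates already recorded. The first two steps below do most of the work.

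1. **SAP 3.3.1.** State that treatment-emergent status is derived from the event's own onset, never from a hospital admission date, and keep the existing clause on worsening after IP starts.
2. **Query before lock.** Review every SAE whose recorded onset equals the index admission date or precedes IP initiation, and ask the site when the event first met a serious criterion. The second condition needs only dates already on the record. Because collection starts at IP initiation, few legitimate records should meet it.
3. **Protocol 8.2.5 or the eCRF Completion Guidelines.** Limit admission and discharge dating to new admissions after IP initiation. For an event that prolongs the existing stay, take onset as the date it met a serious criterion and resolution under the section's general rule.

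The cost is one sentence in the SAP, one in the protocol or guidelines, and one targeted query. No new assessments are needed.

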8.2.6 Fatal Outcome

Any SAE that results in the participant's death (i.e., the SAE was noted as the primary cause of death) must have fatal checked as an outcome, with the date of death recorded as the resolution date. For all other events ongoing at the time of death that did not contribute to the participant's death, the outcome should be considered not resolved, without a resolution date recorded.

For any SAE that results in the participant's death or any ongoing events at the time of death, unless another IP action was previously taken (e.g., the IP was interrupted, reduced, or withdrawn), the action taken with the IP should be recorded as "dose not changed" or "not applicable" (if the participant never received the IP). The IP action of "withdrawn" should not be selected solely as a result of the participant's death.

